1.1.3.1 Pharmacokinetics and Pharmacodynamics

In the previous phase II AD study (12936A), the estimated mean idalopirdine maximum concentration (C_{max}) and the area under the curve (AUC_{0-24h}) following a 30 mg three times daily (TID) dosing regimen were 540 ng/mL and 11700 h*ng/mL, respectively. Based on the same population PK model, the estimated exposures following the 30 mg once daily and 60 mg once daily dosing regimens will be mean C_{max} 180 ng/mL and 390 ng/mL, and mean AUC_{0-24h} 3170 h*ng/mL and 6930 h*ng/mL, respectively.

Donepezil is mainly metabolised by CYP3A4 and to a minor extent by CYP2D6. In study 12936A, the estimated impact of idalopirdine CYP2D6 inhibition on donepezil clearance was in agreement with the observed donepezil exposure at Week 4 and onwards (10% reduction in clearance). In the current study, the impact on donepezil clearance and exposure is expected to be of the same order of magnitude or slightly lower, due to the decreased dose.

The doses in the current phase III clinical program and present study have been selected based on the data from a clinical 5-HT6 receptor occupancy study (in reporting) and simulations in AD patients. 30mg/day and 60 mg/day idalopirdine are predicted to be the clinically effective doses based on the high 5-HT6 receptor occupancy.

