5.3 Selection Criteria

Patient selection is based on the inclusion and exclusion criteria listed below.

Patients who meet each of the inclusion criteria at the Baseline II Visit and none of the exclusion criteria at the Baseline II Visit are eligible to participate in this study.

Open-label treatment period (initial 28-week period):

Inclusion Criteria

- 1. The patient has completed Visit 7 (Completion Visit) in the lead-in study.
- 2. The patient's sight and hearing (hearing aid permissible) are, in the investigator's judgement, sufficient for compliance with the study procedures.
- 3. The patient (and/or if applicable the legal representative if different from the responsible caregiver) and the responsible caregiver are able to read and understand the *Informed Consent Form*.
- 4. The patient (and/or if applicable the legal representative if different from the responsible caregiver) and the responsible caregiver have signed the *Informed Consent Form*.
- 5. The patient is willing and able to attend study appointments within the specified time windows.
- 6. The patient has a knowledgeable and reliable caregiver who will accompany the patient to all clinic visits during the study.
- 7. The patient, if a man, must:
 - use two methods of contraception in combination if his female partner is of childbearing potential; this combination of contraceptive methods must be used from the Baseline II Visit to ≥1 month after the last dose of IMP, OR
 - have been surgically sterilised prior to the Completion Visit in the lead-in study.

Exclusion Criteria

- 1. The patient has experienced seizures before Completion Visit in the lead-in study.
- 2. The patient has evidence of clinically significant disease including but not limited to pulmonary, gastrointestinal, renal, hepatic, endocrine or cardiovascular system disease or metabolic disturbance (patients with controlled diabetes, or patients with controlled hypertension, or right bundle branch block, complete or partial, may be included in the study). Patients with pacemakers are eligible provided that they follow a routine check-up with their doctor and are considered stable. As specified in the donepezil *summary of product characteristics (SmPC)* special precaution is needed for patients with asthma, obstructive pulmonary disease, bradycardia, or difficulty in passing urine.

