- 3. The patient takes or has taken disallowed recent or concomitant medication (specified in Appendix II) or it is anticipated that the patient will require treatment with at least one of the disallowed concomitant medications during the study.
- 4. The patient's donepezil treatment is likely to be interrupted or discontinued during the study.
- 5. The patient is receiving therapy with another AChEI or memantine.
- 6. The patient has clinically significant abnormal vital signs at the Completion Visit in the lead-in study considered a potential safety risk by the Investigator.
- 7. The patient has a moderate or severe on-going adverse event from the lead-in study considered a potential safety risk by the investigator.
- 8. The patient has been tested positive for hepatitis B surface antigen (HBsAg), or hepatitis C virus/antibodies (anti-HCV), AND had abnormal ALT, AST or bilirubin in the lead-in study.
- 9. The patient has been tested positive for hepatitis B surface antigen (HBsAg), or hepatitis C virus/antibodies (anti-HCV) for the first time within the last 6 months prior to the Completion Visit in the lead-in study.
- 10. The patient has one or more clinical laboratory test values outside the reference range, based on the latest blood and urine sample results, available at the Completion Visit in the lead-in study, that are of potential risk to the patient's safety, or the patient has according to the latest available blood sample:
 - a serum creatinine value >1.5 times the upper limit of the reference range, or
 - a serum total bilirubin value >1.5 times the upper limit of the reference range, or
 - a serum alanine aminotransferase (ALT) or aspartate aminotransferase (AST) value >1.5 times the upper limit of the reference range.
- 11. The patient has, based on the latest ECG results, available at the Completion Visit in the lead-in study:
 - an abnormal ECG that is, in the investigator's opinion, clinically significant, or
 - a heart rate <45 beats per minute, or
 - a PR interval >280 ms, or
 - a QRS interval >150 ms, or
 - a QTcF interval >480 ms (based on the Fridericia correction where $QTcF = QT/RR_{0.33}$)

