Patients with a heart rate between 45 and 49 beats per minute or a PR interval between 250 and 280 ms, based on the latest ECG results, available at the Completion Visit in the lead-in study, must be discussed with the sponsor medical expert before being enrolled. The patients can be considered eligible, provided they are stable and there is no safety risk related to their participation in the study as per the investigator's judgement.

- 12. The patient is, in the investigator's opinion, unlikely to comply with the protocol or is unsuitable for any reason.
- 13. The patient has attempted suicide within the last 6 months or is at significant risk of suicide (either in the opinion of the Investigator or defined as a "yes" to suicidal ideation questions 4 or 5 or answering "yes" to suicidal behaviour on the C-SSRS within the last 12 months).

Open-label treatment period with memantine (substudy):

Patients who meet each of the inclusion criteria at the Baseline III Visit and none of the exclusion criteria at the Baseline III Visit are eligible to participate in the open-label treatment period with memantine (substudy).

Inclusion Criteria

- 1. The patient has completed Visit 6 [(i.e., the open-label treatment period (initial 28-week period)].
- 2. The patient's sight and hearing (hearing aid permissible) are, in the investigator's judgement, sufficient for compliance with the study procedures.
- 3. The patient (and/or if applicable the legal representative if different from the responsible caregiver) and the responsible caregiver are able to read and understand the *Informed Consent Form*.
- 4. The patient (and/or if applicable the legal representative if different from the responsible caregiver) and the responsible caregiver have signed the *Informed Consent Form*.
- 5. The patient is willing and able to attend study appointments within the specified time windows.
- 6. The patient has a MMSE score at the Baseline III Visit of this study not greater than 19 in accordance with the memantine label/*summary of product characteristics (SmPC*).
- 7. The patient, according to the judgement of the investigator, requires initiation of treatment with memantine as per local label/*SmPC*/treatment guidelines.
- 8. The patient has a knowledgeable and reliable caregiver who will accompany the patient to all clinic visits during the study.
- 9. The patient, if a man, must:

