- 12. The patient has one or more clinical laboratory test values outside the reference range, based on the latest available blood and urine sample results available at Visit 6, that are of potential risk to the patient's safety, or the patient has according to the latest available blood sample:
 - a serum creatinine value >1.5 times the upper limit of the reference range, or
 - a serum total bilirubin value >1.5 times the upper limit of the reference range, or
 - a serum alanine aminotransferase (ALT) or aspartate aminotransferase (AST) value >2 times the upper limit of the reference range
- 13. The patient has, based on the latest ECG available at Visit 6:
 - an abnormal ECG that is, in the investigator's opinion, clinically significant, or
 - a heart rate <45 beats per minute, or
 - a PR interval >280 ms, or
 - a QRS interval >150 ms, or

a QTcF interval >480 ms (based on the Fridericia correction where QTcF = QT/RR0.33)

Patients with a heart rate between 45 and 49 beats per minute or a PR interval between 250 and 280 ms, based on the latest ECG results, available at Visit 6, must be discussed with the sponsor medical expert before being enrolled. The patients can be considered eligible, provided they are stable and there is no safety risk related to their participation in the study as per the investigator's judgement.

- 14. The patient is, in the investigator's opinion, unlikely to comply with the protocol, e.g., unable to complete all relevant assessments including the C-SSRS at Visit 6 or is unsuitable for any other reason (e.g., worsening of the patient's dementia to the degree that a change in the patient's residential status is warranted over the next 6 months).
- 15. The patient is likely to be placed in a nursing home during the study.
- 16. The patient has attempted suicide within the last year or is at significant risk of suicide (either in the opinion of the Investigator or defined as a "yes" to suicidal ideation questions 4 or 5 or answering "yes" to suicidal behaviour on the C-SSRS within the last 12 months).

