Table 3 PCS Criteria for ECG Parameters

CDISC term	Parameter (units)	PCS Criterion Low	PCS Criterion High
Absolute Time Int	erval		
PRMEAN	PR interval (msec)		≥ 260
QRSDUR	QRS interval (msec)		≥ 150
QTMEAN	QT interval (msec)		≥ 500
Derived Time Inte	rval		
QTcB	QTcB interval (msec)	< 300	> 500 or increase > 60
QTcF	QTcF interval (msec)	< 300	> 500 or increase > 60
HRMEAN	ECG Mean heart rate (beats/min)	\leq 50 and decrease \geq 15	\geq 120 and increase \geq 15

Trial Site Number: Study Level

Version: 1.0

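### The SAP's ECG screening rules can miss new heart rates below 45 bpm and, to a smaller extent, new QTcF values above 480 ms, the protocol's own entry limits

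*SAP*

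**What the plan says.** Protocol 5.3 excludes patients from the 28-week period (criterion 11) and from the memantine substudy (criterion 13) who have "a heart rate <45 beats per minute, or" "a QTcF interval >480 ms", among other ECG limits. The substudy criterion uses the latest ECG available at Visit 6, so it is applied to an ECG taken on open-label treatment. A slow but permitted rate gets special attention: "Patients with a heart rate between 45 and 49 beats per minute or a PR interval between 250" and 280 ms must be discussed with the sponsor's medical expert before enrolment.

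SAP Appendix IV, Table 3 sets the PCS limits used in reporting:
- Heart rate, low, in the row "ECG Mean heart rate (beats/min"): at most "50 and decrease" of at least 15 bpm. Both parts are needed. Table 2 has the same joint rule for pulse.
- QTcF, high: above 500 ms, or a rise above 60 ms. QTcB has the same rule.
- QT: 500 ms or more. PR: 260 ms or more. QRS: 150 ms or more.

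SAP 11.2 summarises change-based PCS values in the open-label period against both Baseline I and Baseline II. The PCS listings and the listings of adverse events for PCS patients use Baseline II only. The Panel 5 line plots cover only heart rate and QTcF, for patients who are PCS on those two parameters.

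**The concern.** The primary objective is long-term safety. All patients take donepezil, and protocol 5.3 notes from its label that "special precaution is needed for patients with asthma, obstructive pulmonary disease, bradycardia, or difficulty in passing urine". Protocol 1.1.3.1 adds that idalopirdine slows donepezil elimination ("10% reduction in clearance" in the phase II study), with an effect of the same order or slightly smaller expected here. Slow heart rate is thus a foreseeable question.

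The patient-level ECG outputs (PCS counts, listings and plots) are all selected by the Table 3 rules. A rule needing both a low level and a large fall is least sensitive in patients who start low, the group protocol 5.3 singles out. A patient whose Visit 6 heart rate of 44 bpm bars entry to the substudy may not appear in any heart-rate PCS output. For the other two ECG limits there is no such gap: PR of 260 ms or more covers everything above 280 ms, and QRS of 150 ms or more covers everything above 150 ms.

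**Working it through.** The plan states no figure to reproduce. The check applies the Table 3 rules to every whole-number baseline that the entry criteria allow (heart rate 45 bpm or more, QTcF 480 ms or less).

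**Heart rate.** The low flag needs a value ≤ min(50, baseline − 15).
- Baseline 58: min(50, 43) = 43, so 44 bpm is not flagged. Baseline 59: the limit is 44, so 44 bpm is flagged.
- 44 bpm is missed for baselines 45–58; 40 bpm for 45–54; 35 bpm for 45–49. Only at 30 bpm or below is every eligible baseline flagged.
- Baselines 45 to 49 need 30 to 34 bpm or below.
- Pulse has the same formula, so it is no backstop.

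**QTcF row alone.** The high flag needs a value > 500 or value − baseline > 60.
- 481 ms is missed for baselines 421–480; 490 ms for 430–480; 500 ms for 440–480. From 501 ms all are flagged.

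**QT and QTcB rows.** With QTcF = QT/RR^(1/3), QTcB = QT/RR^(1/2) and RR = 60/HR:
- QT < 500 requires HR > 60 × (QTcF/500)³.
- QTcB ≤ 500 requires HR ≤ 60 × (500/QTcF)⁶.
- At QTcF 490: 60 × 0.98³ = 56.5 and 60/0.98⁶ = 67.7. So 490 ms escapes both absolute limits only at about 56–68 bpm. At 55 bpm, QT = 490 × (60/55)^(1/3) ≈ 504 ms, which is flagged.
- At 481 ms the escaping band is about 53.5–75.7 bpm; at 495 ms, 58.3–63.7 bpm; at 500 ms there is none.
- A QTcB rise above 60 ms can flag further patients.

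**How many patients.** The documents give no heart rate or QTcF distribution, so the following are simulations on assumed inputs, with entry limits applied at baseline and five post-baseline ECGs (Visits 2–6).

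| Assumed inputs | Patients considered | Not flagged |
|---|---|---|
| Heart rate mean 60–68, between-patient SD 9–10, within-patient SD 5–7 bpm | Any value < 45 bpm | 51–83% against Baseline II; 31–72% against Baselines I and II |
| QTcF mean 415–425, between-patient SD 18–22, within-patient SD 10–12 ms | Any value > 480 ms | 95–99% by the QTcF row alone |
| As above, plus an assumed heart rate | Any value > 480 ms | About 41–47% by any of QTcF, QT, QTcB |

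Under the QTcF assumptions, about 3–33 patients would exceed 480 ms, taking as denominator the planned completers: (3×310 + 3×280) × 0.85 × 0.85 = 1278.8, which the SAP rounds to 1280.

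**The case against.** The strongest reply is that entry criteria and PCS criteria do different jobs, and nothing in the documents requires them to match. That stands. PR shows that they were not built to match (260 ms against an entry limit above 280 ms). The 500 ms QTcF cut-off is the value used in the protocol's own withdrawal criterion (5.4). Requiring level and change together is also the SAP's convention for blood pressure and pulse, and it avoids flagging patients who were admitted slow and stayed slow. A reader might infer that the SAP contradicts the protocol; it does not.

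The reply does not dispose of the point. Substudy criterion 13 applies 45 bpm and 480 ms to ECGs taken on treatment. Protocol 9.4.5 also removes from the investigator's final decision the abnormalities in an exclusion criterion numbered 10. Since the ECG criterion is 11, this looks misnumbered; if so, these limits also bear on how on-study ECGs are judged. And counting only new crossings would not flag patients who were already slow.

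A reader might also infer from the QTcF row that nearly every value of 481–500 ms goes unreported. The QT and QTcB rows refute that: patients flagged there enter the PCS summaries and listings, though not the QTcF plots in Panel 5.

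Other safeguards exist. ECGs get a central cardiological interpretation, clinically significant abnormalities become adverse events (protocol 9.4.5), and by-visit summaries include minimum and maximum (SAP 5 and 11.2). They are partial: adverse-event recording depends on a judgement of significance, and an extreme value is not a patient count. The clinical prior is modest too. The 10% figure came from 90 mg/day, and the phase II ECG changes were small and without trends (protocol 1.1.3.3).

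**Conclusion.** The point holds as a gap in sensitivity in a descriptive safety analysis. The heart-rate half is the stronger. It follows from the rule itself that 44 bpm is unflagged against Baseline II for every baseline of 45–58 bpm, and that patients admitted at 45–49 bpm must reach 30–34 bpm or below. Using Baseline I as well narrows the gap in the summaries and plots, but not in the listings. The QTcF half is real but smaller, because QT and QTcB catch part of it.

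The rule-based results need no assumptions. The percentages rest wholly on assumed distributions and show only that the gap could affect a substantial share of the patients who cross the limits. It would go too far to say that new bradycardia or QTcF prolongation is mostly invisible in the outputs. It is often not flagged.

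**What to change.** Keep every existing PCS row. Add to SAP 11.5 and Table 3 two descriptive counts (n and %) for each treatment period:
- patients with any post-Baseline II (or post-Baseline III) heart rate below 45 bpm, among those not below 45 bpm at that period's baseline;
- patients with any post-Baseline II (or post-Baseline III) QTcF above 480 ms, among those not above 480 ms at that period's baseline.

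Include these patients in the PCS listings, the listings of adverse events for PCS patients, and the Panel 5 plots.

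With this change, 58 to 44 bpm, 48 to 36 bpm and 450 to 490 ms would all be counted. The data are already collected, and no clinical rule changes. The cost is a table edit, minor programming and some more flagged patients to review.
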